8.4.1.2 Adverse Events

Treatment emergent adverse events will be summarized in an overall summary presenting the number (%) of subjects with:

- any AE,
- AE grade 2 or higher (at least moderate in severity),
- AE grade 3 or higher (at least severe in severity),
- treatment related AE,
- AE related to autoimmunity,
- AE leading to study discontinuation,
- any serious adverse event (SAE),
- treatment related SAE,
- SAE related to autoimmunity,
- SAE leading to death.

Incidence and frequency of treatment emergent AEs will be summarised by system organ class (SOC) and preferred term (PT):

- overall,
- by maximum severity,
- treatment related AEs,
- SAEs (if sufficient events),
- AEs leading to study discontinuation (if sufficient events).

In addition, a summary table for the most frequently reported treatment emergent adverse events (those reported in 2 or more subjects) will be presented by PT in descending order of incidence and frequency.

In each table, if the same SOC or PT is reported on multiple occasions for a single subject, it will only be included once in the summary. In the table by maximum severity, only the most severe occurrence for each SOC and PT for each subject will be included in the summary. In the table by maximum relationship, only the most related occurrence for each SOC and PT for each subject will be included in the summary.

Any adverse events that are not treatment emergent (occurred prior to the infusion) will be listed.

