1.4.2.2 Potential Risks Related to Bone Marrow Harvesting

CD34+ cells will be isolated from BM. There is potential risk associated with the BM harvesting procedures, which entails general anaesthesia, multiple percutaneous aspirations from the posterior pelvic bone and a blood cell transfusion.

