1.4.2.3 Potential Risks Related to Concomitant Therapy

Busulfan

Busulfan is used for conditioning prior to the re-infusion of the HSCs. The Busulfan dose to be used in this clinical study will target a specific area under the curve (AUC), which will ensure more precise dosing and may reduce the risks of toxicity. The risks attached to Busulfan are minimal, although there is a very small possibility of Busulfan-related cancer.

More common risks associated with Busulfan at higher doses include nausea, vomiting, diarrhoea, constipation, loss of appetite, mouth sores, stomach/abdominal pain, dizziness, swelling ankles/feet/hand, flushing, headache, trouble sleeping and a period of neutropaenia. However, the above systemic side-effects have not been seen at the proposed Busulfan dose for this study.

In the Sponsor's experience to date, there have been no Busulfan-related serious adverse events (SAEs).

Pegylated-ADA

The withdrawal of PEG-ADA, which is required 1 month after OTL-101 administration, can have adverse effects on immunity, as well as on other organ systems. It is possible that a very severe infection may develop during this time, which could be fatal if the subject does not respond to OTL-101 infusion.

In the Sponsor's experience to date, there have been no severe infections nor causalities, related to stopping PEG-ADA ERT, 1 month after OTL-101 infusion as per protocol.

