8.1 Safety Endpoints

The safety and tolerability of OTL-101 will be assessed throughout the study by evaluating AEs, clinical laboratory test results, vital signs measurements, ECG, physical examination results, and concomitant medication usage. This will include the occurrence of events related to safety:

- Grade 3/4 procedure-related AEs, including GvHD.
- Episodes of severe and opportunistic infections.
- Clinical laboratory toxicities, including myelosuppression, abnormal blood cell counts and/or biochemistry parameters, according to AE grading scale described in [Section 8.2.1.4](#).
- Toxicity related to the use of LV, specifically the emergence of replication competent lentivirus or monoclonal expansion or leukemia, due to vector insertion.

The safety assessments are described in [Section 8.2](#).

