8.2 Safety Assessments

8.2.1 Adverse Events

Adverse events will be monitored and recorded from the time that the subject's parents/legal guardians provide informed consent and then throughout the study (see [Section 3.5](#) for definition of the study duration) and will be elicited by direct, non-leading questioning or if spontaneously reported by the subject/parent/legal guardian. Further details on AE reporting can be found in [Section 8.2.2](#).

An AE is the development of an undesirable medical condition or the deterioration of a pre-existing medical condition following or during exposure to a pharmaceutical product, whether or not it is considered to be causally related to the product. An undesirable medical condition can be symptoms (e.g. nausea, chest pain), signs (e.g. tachycardia, enlarged liver) or the abnormal results of an investigation (e.g. laboratory findings, ECG). In clinical studies an AE can include an undesirable medical condition occurring at any time, including run in or washout periods, even if no OTL-101 has been administered.

Death due to disease progression will be recorded as part of the efficacy evaluation (due to failure of the OTL-101 product) and will be regarded as an SAE unrelated to OTL-101.

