8.4.1.1 Definition of Treatment-emergent Adverse Events

Adverse events (AEs) will be summarised on the basis of treatment emergence. An adverse event is considered to be treatment emergent if it occurred on or after the date and time of the

start of the IMP infusion. If the start time of the event is not present, any event starting on the same day as the infusion will be considered to be treatment emergent. If the start date of the adverse event is partial or missing, it will be considered to be treatment emergent if:

- the day is missing, the month and year are present and are the same as or after the month and year of the infusion and the end date is missing or is not before the date of infusion,
- the day and month are missing, the year is present and is the same as or after the year of the infusion and the end date is missing or is not before the date of infusion,
- the entire date is missing and the end date is missing or is not before the date of infusion.

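### Acute adverse events of the bone marrow harvest and the Busulfan days enter no incidence table, and procedure-related events after infusion are counted without being identified

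*SAP*

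**What the plan says.** **Collection.** Protocol 8.2.1 starts at consent: "Adverse events will be monitored and recorded from the time that the subject's parents/legal guardians provide informed consent and then throughout the study". The schedule of events (SAP Table 1) marks AEs at the pre-harvest, harvest, baseline and both Busulfan assessments.

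**Endpoint.** Protocol 8.1 includes among the safety events "Grade 3/4 procedure-related AEs, including GvHD". The protocol does not define procedure-related, and its list of safety endpoints in 9.3.4 does not repeat the item. Protocol 8.2.1.2 has two causality categories, related and not related, and both refer to OTL-101 administration.

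**Analysis.** SAP 8.4.1.1 states: "Adverse events (AEs) will be summarised on the basis of treatment emergence". Emergence means onset at or after the start of the infusion. SAP 8.4.1.2 then sets out an overall summary, with a row that begins "AE grade 3 or higher (at least severe in severity", and tables introduced by "Incidence and frequency of treatment emergent AEs will be summarised by system organ class (SOC) and preferred term (PT". All of these are restricted to treatment-emergent events. The section closes with "Any adverse events that are not treatment emergent (occurred prior to the infusion) will be listed".

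**Timing.** SAP Table 1 puts the harvest about 30 days before the infusion visit. Protocol 6.2.1.1 puts the two Busulfan doses on Day -4 or -3 and Day -2 or -1, with at least 24 hours between the end of Busulfan and the infusion.

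**The concern.** No child can receive OTL-101 without a harvest and conditioning, and Protocol 5.1.2 allows a second harvest if the first yields too few cells or the product fails release. On the harvest, Protocol 1.4.2.2 says "There is potential risk associated with the BM harvesting procedures" and refers to general anaesthesia, repeated aspiration and transfusion. On Busulfan, Protocol 1.4.2.3 says "More common risks associated with Busulfan at higher doses include nausea, vomiting". That sentence concerns higher doses. The same section says those systemic effects have not been seen at this study's dose and that the sponsor has had no Busulfan-related serious AE so far.

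This trial would be the natural source for updating that experience. Protocol 5.1.4 adds that exposure-adjusted conditioning is possible only because the product is cryopreserved, so the conditioning days are part of what is new here. A serious or Grade 3/4 event on those days, or around the harvest, would still appear in no count. A reader who takes the reported rates as the safety of the whole course would be reading a profile that starts only at the infusion.

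**Working it through.** The plan gives no figure on this point, so there is none to reproduce. The check applies the written rules to example events and then does one piece of arithmetic.

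**Step 1. Which events reach an incidence table?** Inputs: the emergence rule in SAP 8.4.1.1, the emergence rule in Protocol 9.6.5, and the timing above.

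| Example Grade 3/4 event | SAP rule | Protocol rule | Where it appears under the SAP |
|---|---|---|---|
| Harvest event, about Day -30 | Not emergent | Not emergent | Listing only |
| First Busulfan dose, Day -3 | Not emergent | Not emergent | Listing only |
| Second Busulfan dose, Day -1 | Not emergent | Not emergent | Listing only |
| Infusion reaction, Day 0 | Emergent | Emergent | Grade 3+ row and maximum-severity table, unlabelled |
| Busulfan cytopenia, onset Day +8 | Emergent | Emergent | Grade 3+ row and maximum-severity table, unlabelled |

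An event that starts on Day -1 and worsens after infusion is emergent under the protocol but not under the SAP. That mismatch needs its own reconciliation and is not part of this point.

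**Step 2. Is there another route into a table?**
- SAP 8.2.12 to 8.2.14 (harvest, Busulfan administration, Busulfan pharmacokinetics) summarise no AEs.
- The treatment-related rows cannot stand in for procedure-related ones, because relatedness is judged against OTL-101 only. The overall summary does have rows for autoimmunity, so a cause-specific row would fit its format.
- Protocol 9.6.5 could be read as tabulating all serious AEs. The SAP limits its serious AE table by system organ class and preferred term to treatment-emergent events, and produces it only if there are enough of them.
- Under SAP 8.4.1.1 an event with a partial or missing start date may default to emergent. This is a narrow exception.

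**Step 3. Size.** The Grade 3+ row counts subjects, not events. Let k of the 10 planned infused children have a Grade 3 or higher event after infusion. The planned row shows k/10. Suppose one child has a Grade 3/4 event before infusion, and count both periods together:
- if that child is already among the k: k/10 - k/10 = 0;
- if not: (k + 1)/10 - k/10 = 1/10, or 10 percentage points.

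The change is therefore 0 to 10 points. The documents give no event rate that would narrow it. Protocol 3.6.1 treats transient Grade 4 hematologic toxicity from Busulfan as anticipated. The more children who have that recorded as an AE after infusion, the more often the change is 0.

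**The case against.** The case for leaving the SAP alone has several parts.

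- Treatment-emergent tables with a listing of earlier events are a usual arrangement, and Protocol 9.6.5 also ties emergence to the OTL-101 infusion. This stands: the SAP does not depart from the protocol in anchoring its main tables there, and those tables should not change.
- No event is lost. Each appears in a listing, the protocol plans listings by subject, system organ class and preferred term, and a reader can count ten children by hand. This stands as far as it goes, but a listing reports no rate and leaves the count to each reader.
- The items in Protocol 8.1 are unranked and sit under the safety of OTL-101. The mention of graft-versus-host disease points at least partly to the transplant, and 9.3.4 omits the item. This shows that the term is unclear. It does not show that harvest and conditioning are excluded.
- The pre-infusion window is not blank. The SAP summarises coagulation tests (8.2.6), transfusion at harvest (8.2.12), active infection by visit (8.4.3) and laboratory values with a baseline (8.4.6). That is correct, but none of these is an AE summary.
- A full table by organ class and preferred term over several periods would be nearly empty at N=10. This stands and limits what should be asked for.

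**Conclusion.** The point holds in a limited form. In infused children, AEs of the harvest and of the Busulfan days that start before infusion enter no incidence table. Grade 3/4 procedure-related AEs, which Protocol 8.1 names, have no summary of their own. The second gap has two causes: the listing rule, and a causality scale that does not record relationship to a procedure. Tabulating the earlier events would not by itself deliver that endpoint.

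A reader might infer more than the documents support:
- *That procedure-related events are never tabulated, or that all Busulfan toxicity is outside the tables.* Those with onset from infusion onward are counted, only without a label.
- *That each uncounted event lowers the Grade 3+ rate by 10 points.* That is the upper end of a 0 to 10 point range.
- *That the published profile will look better than it should.* No rate of harvest or conditioning events is given, and Protocol 1.4.2.3 reports favourable experience at this dose. The omission is certain; its effect on the results is unknown.

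The size assumes ten infused children and one affected child. The conclusion assumes that the SAP is followed as written. It bears on safety reporting only and does not touch the efficacy analyses.

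**What to change.** **SAP 8.4.1.2, one added table.** Keep the treatment-emergent tables as they are. Show the number (%) of infused children with any AE, a Grade 3 or higher AE and a serious AE, by onset period: consent to harvest; harvest to Busulfan start; Busulfan start to infusion; infusion onward. Each child counts once per period, so the columns should not be added together. If the harvest period opens at the start of the first harvest, any second harvest before conditioning falls in the second column. Leave organ-class and preferred-term detail in the listing where a period is sparse.

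The cost is a paragraph of SAP text and one short, sparse table. Onset dates, grades and seriousness are already collected.

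**Procedure-related row, conditional.** Add a Grade 3/4 procedure-related row only after the sponsor has defined the term and stated how events are attributed. Examples are onset-window rules fixed without reference to outcomes, or medical review of existing records. This costs more than SAP wording, because the current causality scale does not hold the information.

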8.4.2 Concomitant Medications

Concomitant medications taken during the study will be listed.

8.4.3 Infectious Episodes

Number (%) of subjects with an active infection will be summarized at each visit along with the number (%) with each type/location of infection. In addition, an overall summary of the number (%) of subjects with an active infection and each type/location of infection at any time post-infusion will be presented.

8.4.4 Replication Competent Lentivirus (RCL) Testing

Number (%) of subjects testing positive for RCL will be summarized by visit and at any time.

8.4.5 Leukaemia Assessment

Blood samples for leukaemia assessments will be taken over time. The number (%) of subjects with potential leukoproliferation will be summarized by visit and at any time post-infusion.

The number (%) with a bone marrow sample taken, with morphology assessed, with an abnormal morphology assessment, tested for integration analysis and with an abnormal assessment for integration analysis will be summarized by visit and at any time post-infusion.

8.4.6 Laboratory Evaluations

8.4.6.1 Haematology

Haematology parameters (red blood cell (RBC) count, hemoglobin, hematocrit, mean corpuscular volume (MCV), mean corpuscular hemoglobin (MCH), mean corpuscular hemoglobin concentration (MCHC), white blood cell count (WBC), neutrophils, lymphocytes, monocytes, eosinophils, basophils and platelet count) will be evaluated over time. The baseline evaluation for each parameter will be the final evaluation prior to the OTL-101 infusion.

For each parameter, the actual value and change from baseline will be summarized at each visit using descriptive statistics.

Hematology evaluations will be flagged against the normal range as low/normal/high. For each parameter, the number (%) of subjects with evaluations that were low/normal/high relative to the normal range will be summarized by visit. In addition, shift tables will be constructed comparing the flags at the baseline evaluation with the minimum and maximum evaluation post-infusion. Out of range values will be assessed for their clinical significance. For each parameter, the number (%) of subjects with clinically significant evaluations will be summarized by visit and at any time post-infusion.

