8.2.1.4 Laboratory Test Abnormalities

Abnormalities in laboratory test values should only be reported as AEs if any of the following apply:

- They result in a delay of the OTL-101 treatment or other study procedures,
- They require an intervention or diagnostic evaluation to assess the risk to the subject,
- They are considered to be clinically significant by the Investigator.

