7.2 Safety Population

The safety population will consist of all subjects treated with OTL-101 within this protocol.

8 Statistical Methods

In general, continuous variables will be summarized using the mean, standard deviation, minimum, median, maximum and number of subjects. Categorical variables will be summarized using number of subjects and percentages.

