8.4.6.2 Biochemistry

Biochemistry parameters (blood urea nitrogen, creatinine, total bilirubin, sodium, potassium, chloride, calcium, aspartate transaminase (AST), alanine transaminase (ALT), alkaline phosphatase (ALP), albumin, total protein, glucose, magnesium, phosphates) will be evaluated over time. The baseline evaluation for each parameter will be the final evaluation prior to the OTL-101 infusion.

For each parameter, the actual value and change from baseline will be summarized at each visit using descriptive statistics.

Biochemistry evaluations will be flagged against the normal range as low/normal/high. For each parameter, the number (%) of subjects with evaluations that were low/normal/high relative to the normal range will be summarized by visit. In addition, shift tables will be constructed comparing the flags at the baseline evaluation with the minimum and maximum evaluation post-infusion. Out of range values will be assessed for their clinical significance. For each parameter, the number (%) of subjects with clinically significant evaluations will be summarized by visit and at any time post-infusion.

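### The analysis plan does not grade laboratory values, so the graded laboratory toxicity named in Protocol 8.1 is tabulated only for abnormalities reported as adverse events

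*SAP*

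**What the plan says.** Protocol 8.1 lists among the safety endpoints: "Clinical laboratory toxicities, including myelosuppression, abnormal blood cell counts and/or biochemistry parameters, according to AE grading scale described in" Section 8.2.1.4. That section contains no scale. It sets out when a laboratory abnormality counts as an AE: "Abnormalities in laboratory test values should only be reported as AEs if any of the following apply". The grounds are a delay to treatment or procedures, a need for intervention or diagnostic work-up, or the investigator's view that the result matters clinically.

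The SAP plans four outputs for haematology (8.4.6.1) and the same four for biochemistry (8.4.6.2):

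- Descriptive statistics: "For each parameter, the actual value and change from baseline will be summarized at each visit using descriptive statistics". The opening of SAP Section 8 defines these: "continuous variables will be summarized using the mean, standard deviation, minimum, median, maximum and number of subjects".
- Flags: "Hematology evaluations will be flagged against the normal range as low/normal/high" and "Biochemistry evaluations will be flagged against the normal range as low/normal/high".
- Flag shifts: "shift tables will be constructed comparing the flags at the baseline evaluation with the minimum and maximum evaluation post-infusion".
- Clinical significance: "the number (%) of subjects with clinically significant evaluations will be summarized by visit and at any time post-infusion".

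Protocol 9.6.5 plans summary statistics, flagged listings and low/normal/high shift tables. It plans no grade table either. In the SAP, grades appear only in 8.4.1.2, for treatment-emergent AEs.

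**The concern.** The endpoint calls for severity on a scale, but the laboratory tables carry only direction relative to a normal range. The one graded output depends on whether someone chose to report the abnormality as an AE.

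Severity and timing of cytopenia matter in this trial. Subjects receive Busulfan, and Protocol 1.4.2.1 names as a risk that the cryopreserved product may work less well and that back-up marrow may be needed. Protocol 3.6.1 distinguishes Grade 4 events, and haematologic events that resolve within 42 days. A reader of the safety tables would want to know how many children reached each grade and when. No planned laboratory table says so.

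**Working it through.** The plan states no figure on this point, so the check sets the endpoint against the outputs and then tests what a flag can distinguish.

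**1. What each planned output delivers**

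| Output | Gives | Does not give |
|---|---|---|
| By-visit statistics (SAP 8, 8.4.6) | Lowest, median and highest value at each visit | Number of subjects per grade; each subject's worst value |
| Flags by visit | Number low, normal, high | Severity within low or high |
| Flag shift to post-infusion minimum and maximum | Direction of each subject's extreme value | Severity of that value |
| Clinical-significance count | Investigator judgement | A grade |
| AE tables (SAP 8.4.1.2) | Grade ≥2, grade ≥3, maximum severity by SOC/PT | Grades of abnormalities not reported as AEs |

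**2. Flags against grades**

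Inputs are the limits in Protocol Appendix 4. The neutrophil row for more than 7 days of age applies, since entry is at 30 days or older.

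- Neutrophils per mm³: Grade 1 is 800–1,000, Grade 2 is 600–799, Grade 3 is 400–599, Grade 4 is <400.
- Platelets per mm³: Grade 1 is 100,000 to <124,999, Grade 4 is <25,000.

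Rule: a count x reads low when x < L, where L is the laboratory's lower limit. The documents give no value of L.

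- Assume L ≥ 1,000. Neutrophil counts of 900, 700, 450 and 150 are Grades 1, 2, 3 and 4, and all four read low.
- Assume a platelet limit of 125,000 or more. All four platelet grades then read low.
- If L were smaller, some mild counts would move to normal. For any neutrophil limit above 400, however, Grade 3 counts between 400 and L still share the low category with Grade 4.

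**3. By-visit minima**

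Take 10 subjects at one visit, with minimum below 400 and median at or above 400. The median of 10 values is the average of the 5th and 6th ordered values. If six or more values were below 400, the 5th and 6th would both be below 400, and so would the median. So at most five are below 400, and the minimum shows at least one is. Minimum and median together therefore allow anything from 1 to 5 subjects at Grade 4. Mean and SD may narrow this but do not state the count. Nor do summaries from separate visits show whether the low values belong to the same child.

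**4. Which scale**

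- Protocol 8.1 points to 8.2.1.4, which has none.
- Protocol 8.2.1.1 uses an adapted NIAID AIDS Division scale and cites Appendix 3; the DAIDS table is printed as Appendix 4.
- Protocol 9.3.4 says CTCAE.

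A grade table cannot be programmed until these agree.

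**5. Are the data there?**

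Haematology is scheduled at Days 1, 4, 8, 11, 15, 19 and 24, Month 1 and Day 42 (9 counts), then at Months 3, 6, 9, 12, 18 and 24 (6 counts). The flag shift table already requires each subject's post-infusion minimum and maximum. Grading those values needs no new collection.

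**The case against.** The strongest reply is that the endpoint is delivered through AEs. Protocol 8.1 itself refers to 8.2.1.4, the AE-reporting rule. Protocol 9.3.4 defines the safety endpoints as graded AEs, and SAP 8.4.1.2 tabulates them by maximum severity. A life-threatening cytopenia would very likely meet one of the reporting grounds. The SAP also follows Protocol 9.6.5, so the inconsistency starts within the protocol. In a descriptive study of 10 subjects, listings and by-visit minima let a careful reader find the worst values by hand.

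Most of this stands, and it limits the size of the point. It does not remove it. Protocol 8.1 lists laboratory toxicity separately from Grade 3/4 procedure-related AEs, which suggests it is more than a subset of them. Reporting on selective grounds is also not the same as grading the laboratory data.

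Some stronger readings are tempting, and the documents do not support them:

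- *Laboratory data appear only as low/normal/high.* Actual values, changes from baseline and clinical significance are summarised as well.
- *Nearly every child will read low after Busulfan.* No rate is given. Protocol 3.6.1 calls transient cytopenias anticipated. Protocol 1.4.2.3 lists neutropenia among effects at higher doses and says the listed systemic effects have not been seen at the study dose. Those two passages must be reconciled.
- *Lymphocytes are low at baseline in everyone.* In Protocol 4.1 lymphopenia is one of several alternative criteria, judged before immune restorative therapy, and Protocol 6.2.1.1 has all subjects on PEG-ADA before infusion.
- *Recovery cannot be seen.* The by-visit summaries can show it over time.
- *A grade table would settle the halting rule.* That rule requires attribution to treatment and discussion with the DSMB. Its definition of failed reconstitution (ANC <200/µl or platelets <20,000/µl) also differs from the Grade 4 limits.

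**Conclusion.** The point holds as a moderate reporting gap. A declared safety endpoint asks for graded laboratory toxicity. No planned output gives each subject's worst laboratory grade or the number of subjects per grade, except for abnormalities that became AEs. The gap lies between Protocol 8.1 on one side and Protocol 9.6.5 and SAP 8.4.6 on the other.

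That all four grades collapse into low assumes lower limits above the Grade 1 bands. That Grades 3 and 4 of neutropenia overlap needs only a lower limit above 400/mm³. Neither statement depends on how many children become cytopenic. The primary efficacy results are unaffected. The change should be made because it is cheap and delivers something the protocol says it will report.

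**What to change.** 1. **Settle the scale.** Reconcile Protocol 8.1, 8.2.1.1 and 9.3.4, correct the cross-references, and name one scale and version in the SAP.
2. **Add grade tables** to SAP 8.4.6.1 and 8.4.6.2: worst post-infusion grade per subject, and baseline grade against worst post-infusion grade, for every gradable parameter in each direction. Align Protocol 9.6.5.
3. **Split haematology** into values up to Day 42 and values after it, assigned by actual sample date.
4. **List every Grade 3 or 4 value** with its date.
5. **Keep low/normal/high flags** for parameters or ages without a grade.

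The cost is SAP wording and programming. There are three limits:

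- Some parameters stay ungraded. Appendix 4 grades lymphocyte counts only above 5 years of age and has no row for chloride or total protein. Magnesium and phosphate are not scheduled after infusion.
- Duration is only loosely observable after Day 24. Scheduled counts are then 6 days apart (Day 24 to 30), 12 days apart (Day 30 to 42), and about 49 days apart to Month 3 (3 × 365.25/12 ≈ 91; 91 − 42 = 49). Dates should therefore be listed rather than durations estimated.
- The table shows grade, not cause, and should say so in a footnote. The scheduled baseline count (Day −10 to −4) comes before Busulfan conditioning is completed, so the shifts will include its effect.
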